5.1 Description

The study device is a rTMS HAC-coil manufactured by Brainsway™ to target the dACC. This will be used with the Magstim Rapid Stimulator. The coil and the stimulator are the major components of the system. Stimulation paradigm can be programmed before the patient arrives to deliver trains at a specific frequency. See section 1.2 or the attached manual for details.

5.2 Treatment Regimen

Patients will undergo 3 weeks (5x per week) of high-frequency (10-Hz) rTMS at the dACC interspersed with EEG and neuroimaging acquisitions. The protocol will be administered at the Psychiatric Institute. The intensity of stimulation will be based on resting-motor threshold (RMT). If the patient is unable to tolerate the intensity, this parameter may be reduced to make the patient more comfortable.

5.3 Prior and Concomitant Therapy

- See section 4.

5.4 Receiving, Storage, Dispensing and Return

5.4.1 Receipt of Study Device

The device is currently on the medical campus.

5.4.2 Storage

The stimulation set-up is currently housed at the New York State Psychiatric Institute on the third floor. Trained investigators or physicians will have access to the setup and will administer the stimulation. A physician will be present during rTMS sessions to ensure patient safety.

6 Study Procedures

	Monday	Tuesday	Wednesday	Thursday	Friday
Baseline	Neuroimaging, Neurophysiology and Neuropsychiatry evaluations				
Week 1	rTMS	rTMS preTMS EEG postTMS EEG MMSE, YMRS,CGI, CSSRS	rTMS	rTMS preTMS EEG postTMS EEG YBOCS, MMSE, YMRS, CGI, CSSRS	rTMS
Week 2	rTMS	rTMS preTMS EEG postTMS EEG MMSE, YMRS, CGI, CSSRS	rTMS	rTMS preTMS EEG postTMS EEG YBOCS, MMSE, YMRS, CGI, CSSRS	rTMS
Week 3	rTMS	rTMS preTMS EEG postTMS EEG MMSE, YMRS, CGI, CSSRS	rTMS	rTMS preTMS EEG postTMS EEG YBOCS, MMSE, YMRS, CGI, CSSRS	rTMS
Follow-up	Neuroimaging, Neurophysiology and Neuropsychiatry evaluations				

7 Statistical Plan

Statistical analyses with time series data and factor analysis will be carried out both within subject (to assess reliability of the observed effects across trials) and across subjects (to assess the generalizability across participants). Sample sizes are chosen based on expected effect sizes and the large heterogeneity in this subject population.

8 Safety and Adverse Events

8.1 Definitions

Unanticipated adverse device effect (UADE): Any serious adverse effect on health or safety or any lifethreatening problem or death caused by, or associated with, a device, if that effect, problem, or death was not previously identified in nature, severity, or degree of incidence in the investigational plan or IDE application (including a supplementary plan or application), or any other unanticipated serious problem associated with a device that relates to the rights, safety, or welfare of subjects.

Associated with the investigational device: There is a reasonable possibility that the adverse effect may have been caused by the investigational device.

Life-threatening adverse effect: Any adverse effect that places the subject, in the view of either the investigator or the sponsor, at immediate risk of death from the effect **as it occurred**. It does not include a reaction that, had it occurred in a more severe form, might have caused death.

Serious adverse effect: An adverse effect is considered “serious” if, in the view of either the investigator or the sponsor, it results in any of the following outcomes:

- death
- a life-threatening AE

- inpatient hospitalization or prolongation of existing hospitalization • a persistent or significant disability/incapacity
- a congenital anomaly/birth defect.

Unanticipated adverse effect: Any adverse effect, the nature, specificity, severity, or frequency of which is not consistent with the risk information in the clinical study protocol or elsewhere in the current IDE application.

8.2 Recording of Adverse Device Effects

All observed or volunteered adverse effects (serious or non-serious) and abnormal test findings, regardless of treatment group, if applicable, or suspected causal relationship to the investigational device or, if applicable, other study treatment or diagnostic product(s) will be recorded in the subjects' case histories. For all adverse effects, sufficient information will be pursued and/or obtained so as to permit 1) an adequate determination of the outcome of the effect (i.e., whether the effect should be classified as a serious adverse effect) and; 2) an assessment of the causal relationship between the adverse effect and the investigational device or, if applicable, the other study treatment or diagnostic product(s). Adverse effects or abnormal test findings felt to be associated with the investigational device or, if applicable, other study treatment or diagnostic product(s) will be followed until the effect (or its sequelae) or the abnormal test finding resolves or stabilizes at a level acceptable to the sponsor-investigator.

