1.5 Research Risks & Benefits

1.5.1 Risk of Investigational Device

The risks of rTMS include seizures, headaches, and hearing problems. Since the rTMS induces an electrical field on the brain, the most serious risk is the possibility of having a seizure.

The rTMS coil that is being used in this study is called the "HAC coil". While rTMS has been approved by the FDA for some neuropsychiatric indications such as MDD, this particular coil is experimental and has not yet been approved by the FDA for OCD. Seizures from any kind of rTMS treatment are rare and occur at a rate of about 2/1000. In people who received rTMS in the past with similar intensity and the same Hcoil we will be using in this study, three out of more than 200 people had a seizure. Patients experiencing adverse effects were on certain medications that made them more prone to seizures. In order to minimize the risk for seizures, patients will not be able to participate in this study if they have a medical or psychiatric condition that requires them to take certain medications regularly. Patients will also not be allowed to participate if they have a family history of seizures. A physician will be present during each rTMS treatment and will provide necessary care in case of adverse events. Additionally, suicidal ideation and emergence of manic symptoms following rTMS treatment are also potential risks. Should any of these occur, patients will not be able to continue with the remainder of the study.

There is also a risk of hearing problems (hearing loss or ringing in the ears) after rTMS. This problem is less likely to occur with the proper use of earplugs. The most common risk of rTMS is the possibility of having a headache after the sessions. Over the counter pain medicines (like ibuprofen or acetaminophen) can be taken if needed. Additional risks include scalp and dental pain, which can be treated with over the counter pain medications also. In case of any other adverse events, rTMS will be stopped and patient will be monitored closely.

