3.1 General Design

rTMS delivery: High-frequency (10 Hz) deep TMS will be administered at the dACC to patients over 3 weeks using the HAC-coil (Brainsway™ cingulate coil) designed specifically to target the cingulate cortex and the Magstim Rapid stimulator (Magstim Company Limited, Whitland, UK). Sessions will be administered five times a week with a total of 15 visits. The intensity of stimulation will be relative to resting motor threshold (110%). Forty 3-second trains with an inter-train period of 20 seconds will be applied. Total number of pulses administered will be 1200. Periodic weekly behavioral assessments will be performed with the Yale-Brown Obsessive Compulsive Scale (Y-BOCS) to monitor OCD symptoms. We will also test for suicidal ideation (C-SSRS) and monitor manic symptoms (YMRS) twice a week in addition to baseline and at the end of treatment course (x 8 total) and test cognitive function with Minimental status examination (MMSE). Subjects will be compensated for their daily visits in order to offset inconvenience related to time, effort and transportation costs. They will receive \$100 per fMRI session (x2 total) plus \$40 per TMS session (x15 total) over the study period.

Neuropsychological scales and tests: Neuropsychological evaluations will be administered at baseline and at the end of the study.

1. Scales (expected to take 30-40 minutes total):

- USP-Sensory Phenomena Scale

- Hamilton Depression Rating Scale
- Hamilton Anxiety Rating Scale
- Beck Anxiety Inventory
- Beck Depression Inventory, 2nd Edition
- Sheehan Disability Scale
- Barratt Impulsiveness Scale (BIS -11)
- Clinical Global Impression (CGI)
- Quality of Life Enjoyment and Satisfaction- short form (Q-LES)

2. Neuropsychological measures (expected to take about 90 minutes and can be performed in separate sessions as needed):

- Wechsler Abbreviated Scale of Intelligence (WASI)
- WMS-III Faces, LM, Digit Span, Spatial Span, LNS
- Rey Osterrieth Complex Figure (ROCF)
- California Verbal Learning Test, 2nd Edition (CVLT-II)
- Iowa Gambling Test (IGT)
- Wisconsin Card Sort Task (WCST)
- Judgment of Line Orientation
- Boston Naming Test
- DKEFS Verbal Fluency, Trails, Color Word Interference Test
- Grooved Pegs

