3.2 Primary Safety Endpoints

According to the safety guidelines recommended by Brainsway™ corresponding to the HAC coil, 3 weeks is an acceptable study duration with the investigational HAC-coil. Brainsway™ has performed studies in control subjects and in subjects with clinical conditions (MDD, schizophrenia, bipolar disorder, addiction, PTSD) (Brainsway, Ltd. Unpublished data). They have currently tested 209 subjects (98 without concomitant psychotropic medication; 111 with psychotropic medication) with high-frequency, high-intensity rTMS. Of the subjects who were still taking psychotropic medications that could lower seizure thresholds, 3 suffered a seizure. Should the patient experience adverse effects prior to completion of study, their participation will be discontinued in lieu of their safety. Additionally, we will account for the incidence, severity and frequency of all Adverse Events (AEs), including seizures and suicidality (i.e., suicide attempts and completed suicides).

4 Subject Selection and Withdrawal

CRITERION	METHOD OF ASCERTAINMENT
Inclusion:	
1) Male or female outpatients, 18 to 65 years of age.	Self report
2) Primary diagnosis of Obsessive Compulsive Disorder, as confirmed by the Structured Clinical Interview for the DSM-V-TR (SCID).	SCID, DSM-IV-TR

3) Subjects should have at least a moderate level of OCD severity as defined by a Yale-Brown Obsessive Compulsive Disorder Scale (YBOCS) score of greater than 10 on either obsession section or compulsion section (YBOCS-O \geq 10 or YBOCS-C \geq 10).	YBOCS
3) Patients currently on OCD medication must be at the same stable dose(s) and be willing to continue the same dose(s) through the duration of the study. Note: Subjects should be maintained on SSRI medications (with or without additional antidepressant or psychotropic augmentation for treatment of OCD) at a stable therapeutic dosage for at least 2 months prior to study entry and for the duration of the trial, and/or subjects are maintained on psychotherapeutic behavioral intervention therapy (subjects undergoing CBT treatment must be in the maintenance stage and not in the assessment or skills acquisition or training stages).	Physician Evaluation
4) Patients must continue to be under the care of their treating psychiatrist who will be writing prescriptions for concomitant medications through the duration of the study.	Physician Evaluation
5) Capable and willing to provide informed consent	Physician Evaluation

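### No scheduled adverse-event enquiry is described, so headache, hearing, scalp and dental effects depend on observation or spontaneous report and may be under-estimated

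*Combined protocol and SAP*

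**What the plan says.** Section 8.2 gives the recording rule: "All observed or volunteered adverse effects (serious or non-serious) and abnormal test findings" go into the case histories. Section 8.3.2 uses the same observed-or-volunteered criterion for events that may need reporting to the FDA.

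Section 3.2, headed as the primary safety endpoints, says that "we will account for the incidence, severity and frequency of all Adverse Events (AEs), including seizures and suicidality".

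Section 1.5.1 lists the milder device risks: "The most common risk of rTMS is the possibility of having a headache after the sessions"; "There is also a risk of hearing problems (hearing loss or ringing in the ears) after rTMS"; and "Additional risks include scalp and dental pain, which can be treated with over the counter pain medications also".

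Two risks are sought actively. Section 3.1 says "We will also test for suicidal ideation (C-SSRS) and monitor manic symptoms (YMRS) twice a week", and adds baseline and end of treatment to make 8 assessments. MMSE is also given. In the section 6 schedule, the week 1 Tuesday entry reads "rTMS preTMS EEG postTMS EEG MMSE, YMRS,CGI, CSSRS". Thursdays add the Y-BOCS, and Mondays, Wednesdays and Fridays list stimulation alone.

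**The concern.** The endpoint covers every adverse event, but the protocol describes an active search for only some of them. Headache, tinnitus, and scalp or dental pain are largely subjective, and section 1.5.1 places headache and hearing problems after stimulation. Staff can record such a symptom only if they notice it or the patient raises it. The all-event endpoint therefore combines solicited and unsolicited ascertainment, and the effect that the protocol itself calls most common falls on the unsolicited side.

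This matters because the study has one arm of 15 patients. There is no comparator in which the same shortfall would occur and partly cancel, so the safety result is the absolute count. An under-ascertained count would make the coil look better tolerated than it is. A second difficulty concerns attribution: headache or tinnitus present before treatment cannot be told from an emergent symptom unless it was recorded at the start.

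**Working it through.** The plan states no adverse-event rate, reporting fraction or precision target, so it has no figure of its own to reproduce. The check has two parts.

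**1. What is scheduled.**
- Sessions: 3 weeks × 5 = 15, as section 3.1 states.
- C-SSRS and YMRS: 3 weeks × 2, plus baseline and end = 8 each, as section 3.1 states.
- Adverse-event questions, symptom checklists, pain ratings or hearing tests described in section 3.1 or the section 6 schedule: 0.
- Baseline record of the five symptoms (headache, hearing loss, tinnitus, scalp pain, dental pain): none described. The TASS appears in section 4 as an eligibility screen.
- Severity: section 3.2 promises it. Section 8.1 defines serious and life-threatening effects but gives no grading scale for milder ones.

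**2. How much under-recording could matter.** Illustration only. Let p be the true share of patients with an effect and c the share of those patients in whom it is recorded. Both are assumptions, because the documents give neither. With n = 15:
- expected patients recorded = 15 × p × c
- chance of recording at least one = 1 − (1 − p × c)^15

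| p | c | Expected recorded | Chance of at least one |
|---|---|---|---|
| 0.10 | 1 | 1.5 | 79% |
| 0.10 | 0.50 | 0.75 | 54% |
| 0.10 | 0.25 | 0.375 | 32% |
| 0.30 | 1 | 4.5 | 99.5% |
| 0.30 | 0.50 | 2.25 | 91% |
| 0.30 | 0.25 | 1.125 | 69% |

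Each affected patient who is missed lowers the incidence by 1/15 = 6.7 percentage points. Even with complete capture, no events in 15 patients gives a one-sided 95% upper limit of 1 − 0.05^(1/15) = 18.1%. That limit is valid only if capture is complete, so under-recording would remove the little reassurance that a zero count can give.

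The share c applies to patients. A symptom that recurs gives a patient several chances to mention it, so incidence may suffer less than frequency, for which every occurrence counts.

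**The case against.** The strongest reply is that patients are seen five days a week with a physician present at each session. Section 5.2 allows intensity to be reduced if it is not tolerated, which presupposes some attention to discomfort. Section 8.2 promises to pursue information, and section 8.5 a regular assessment of the number and type of events. Part of this stands: many complaints will probably come up, and discomfort during stimulation may well be noticed. It does not supply a way of finding symptoms that arise after the session. The information pursued under 8.2 concerns the outcome and causality of effects already identified. Section 8.5 gives no method or timing, and counting recorded events does not recover unrecorded ones.

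A second reply is that spontaneous reporting is an acceptable choice in a small feasibility study, and that random error dominates. If 6 of 15 patients were affected and 3 were recorded, the exact 95% intervals would be 16–68% and 4–48%, which overlap heavily. That is true of precision. But under-recording pushes the estimate in one direction, and the intervals make no allowance for it.

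Four stronger readings are tempting, and the documents do not support them:
- *The symptoms are named in the primary safety endpoint.* Section 3.2 names only seizures and suicidality. The milder effects are named in 1.5.1 and are covered by the all-event wording.
- *They are asked about at no visit.* The case report forms, the TASS and the site safety-monitoring plan are not in the text. The items of the Hamilton and Beck scales that section 3.1 lists for baseline and end of study are not reproduced either. The supportable statement is that no enquiry is described.
- *They will be under-counted, by a known amount.* No document gives p or c. The text supports a risk, not a certainty.
- *Patients have a motive to stay silent.* Section 8.4 stops stimulation for any adverse event, and sessions are paid at $40. But section 1.5.1 treats headache, scalp pain and dental pain as manageable with over-the-counter medicine and reserves stopping for other events. The payment is described as offsetting inconvenience. The passages conflict; they do not establish concealment.

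**Conclusion.** The point holds as a risk of bias. As described, ascertainment of the five milder device effects depends on observation or spontaneous report, whereas suicidality and mania are elicited on a schedule. The section 3.2 incidence and frequency for those five effects may therefore be too low, and the text offers no baseline record against which to call a symptom emergent.

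The direction is downward if capture is incomplete; the size cannot be computed from the documents. Under the assumed values shown, halving capture halves the expected count, and for an effect in 10% of patients it lowers the chance of seeing any case from 79% to 54%. The conclusion rests on the protocol text alone. If the unseen forms or monitoring plan already contain a standard query with a baseline, the remaining defect is that the protocol does not say so. This is worth correcting before enrolment, because unreported symptoms and a missing baseline cannot be reliably reconstructed after treatment.

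**What to change.** - In section 8.2, change the criterion to *observed, volunteered or elicited*, and align 8.3.2 with it.
- In the section 6 schedule, add a short fixed checklist: headache, hearing change, tinnitus, scalp pain, dental pain and other, each with severity and onset. Give it at Baseline, at each of the 15 session visits (before stimulation, covering the time since the last visit) and at Follow-up: 1 + 15 + 1 = 17 times. State the severity scale.
- Define an emergent event as new, or worse than the Baseline answer.
- Report elicited and spontaneous events separately.

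The cost is a one-page form and, as an estimate, about two minutes per visit, or 17 × 2 = 34 minutes per patient, at visits that already take place. A checklist records perceived hearing change, not measured hearing. Counts will be higher and less comparable with studies that used spontaneous reports; the separate reporting deals with that.

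A further cost comes from the plan's own wording: more events will be found that meet the text on stopping. Section 8.4 stops stimulation for any adverse event and refers to section 4, whose discontinuation list is narrower. Section 3.2 ends participation for adverse effects. Section 1.5.1 describes headache, scalp pain and dental pain as treatable and links stopping to other events. Read literally, 8.4 could turn common mild symptoms into stopped treatment and erode the paired analysis of 15 patients. The sponsor must reconcile these sections before the checklist is used; which rule should apply is not a matter for this review.

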8.3 Reporting of Adverse Device Effects and Unanticipated Problems

8.3.1 Investigator reporting: Notifying the IRB

The investigator will report any adverse events to the IRB as outlined in the IRB's Unanticipated Problems (UP) Policy.

8.3.2 Sponsor reporting: Notifying the FDA

FDA Reporting Process

For any observed or volunteered adverse event that is determined to be a UADE, the sponsor-investigator will submit an expedited safety report to the FDA's Center for Devices and Radiological Health. The expedited safety report will consist of:

- a completed Form FDA 3500A
- a cover letter analyzing the significance of the event

A copy of this safety report will be provided to all participating study investigators.

The completed Form FDA 3500A and cover letter will be submitted to the FDA as soon as possible and, no, later than 10 working days after the sponsor-investigator first receives notice of the adverse effect.

If, following receipt and investigation of follow-up information regarding an adverse effect that was previously determined not to be a UADE, the sponsor-investigator determines that the event does meet the requirements for expedited reporting, the sponsor-investigator will submit a completed Form FDA 3500A and cover letter as soon as possible, but no later than 10 working days, after the determination is made.

Subsequent to the initial submission of a completed FDA Form 3500A, the sponsor-investigator will submit additional information concerning the reported adverse effect as requested by the FDA. Medical Device Reports, whether for anticipated or unanticipated device-related effects, are to be submitted on FDA Form 3500A. The contact information for submitting MDR reports is noted below:

Food and Drug Administration
Center for Devices and Radiological Health

Medical Device Reporting
[name]
[name]

8.4 Stopping Rules

The patient will be allowed to stop participating in the study at any point. Additionally, any safety considerations will be taken into account and the study will be stopped in accordance with patient comfort. More immediately, rTMS administration will be stopped in the occurrence of any adverse event (See section 4). Regarding the study, we will stop the study if serious AEs are observed in more than 3 subjects.

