6) Signed HIPAA authorization	Physician Evaluation
Exclusion:	
1) Investigators, and their immediate families (defined as spouse, parent, child or sibling, whether by birth or legal adoption).	Self Report
2) Individuals diagnosed by the investigators with the following conditions: Bipolar Disorder (lifetime), any Psychotic Disorder (lifetime), history of substance abuse or dependence within the past year (expect nicotine and caffeine).	Physician Evaluation, SCID, DSMIV-TR
3) An Axis II Personality Disorder, which in the judgment of the investigator may hinder the patient in completing the procedures required by the study protocol.	Physician Evaluation, Private Psychiatrist Reports
4) Individuals with a clinically defined neurological disorder including, but not limited to: stroke, tics, space occupying brain lesion, any history of seizures except those therapeutically induced by ECT, history of cerebrovascular accident, transient ischemic attack within two years, cerebral aneurysm, dementia, Parkinson's Disease, Huntington Chorea, Multiple Sclerosis.	Physician Evaluation, Medical Records
5) Increased risk of seizure for any reason, including prior diagnosis of increased intracranial pressure (such as after large infarctions or trauma), or history of significant head trauma with loss of consciousness for \geq 5 minutes.	Patient Reports
6) History of treatment with rTMS therapy for any disorder.	Patient Reports

Subjects with positive responses to the Transcranial Magnetic Stimulation Adult safety screen (TASS, enclosed)	TASS
7) History of treatment with Deep Brain Stimulation.	Patient Reports
8) Use of any investigational drug within 12 weeks of the randomization visit.	Patient Reports
9) Current use of any medications with proconvulsive action, such as bupropion, maprotiline, tricyclic antidepressant, clomipramine, classical antipsychotics.	Physician Evaluation, Medical Records
10) Inability to obtain a motor threshold in patients due to chronic use of a medication (eg. anticonvulsants, benzodiazepines, sedative/hypnotics and atypical antipsychotics)	Physician Evaluation, Medical Records
11) Significant acute suicide risk, based on the current state or recent history using Columbia Suicide Severity Rating Scale (CSSRS).	C-SSRS
12) Cardiac pacemakers, implanted medication pumps, intracardiac lines, or acute, unstable cardiac disease.	Physician Evaluation

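### The only numeric study-level stop (8.4) need not count a self-limited seizure, or possibly a suicide attempt without admission, although the protocol singles both out

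*Combined protocol and SAP*

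**What the plan says.** Section 8.4 contains one rule with a number: "Regarding the study, we will stop the study if serious AEs are observed in more than 3 subjects". Its other sentences let a patient leave at any time, stop rTMS for any adverse event, and refer generally to safety considerations and patient comfort.

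Section 8.1 calls an adverse effect serious if, "in the view of either the investigator or the sponsor, it results in any of the following outcomes": death, a life-threatening event, "inpatient hospitalization or prolongation of existing hospitalization", persistent or significant disability, or a birth defect. There is no item for other important medical events. Life-threatening requires an immediate risk of death from the event as it happened; an event that would have been fatal only in a worse form is excluded. Section 8.4 speaks of serious AEs and 8.1 of serious adverse effects, but no other definition of serious is given, so 8.1 is the natural reading.

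Elsewhere the protocol gives these events special weight. Section 1.5.1 states that "the most serious risk is the possibility of having a seizure". Section 3.2, on primary safety endpoints, records adverse events "including seizures and suicidality (i.e., suicide attempts and completed suicides"). Section 4 withdraws a subject who has a seizure or attempts suicide after receiving rTMS.

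**The concern.** A seizure that ends by itself, is managed by the physician at the session and leads to no admission can fall outside all five items in 8.1. So might a suicide attempt that is not judged life-threatening and does not lead to admission. Either event withdraws the affected subject, but neither necessarily moves the study toward its one numeric stop. The protocol's own named key harms could recur without that rule registering them, and whether they count would be decided after the event, not before it.

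**Working it through.** **Text check.** The plan states no operating characteristics for the rule, so there is no figure to reproduce. The five items in 8.1, applied to the two events:

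| 8.1 item | Self-limited seizure, no admission | Suicide attempt, no admission |
|---|---|---|
| Death | no | no |
| Life-threatening as it occurred | not necessarily | often, but not necessarily |
| Hospitalization | no | no |
| Lasting or significant disability | not necessarily | not necessarily |
| Birth defect | no | no |

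Either event can therefore add nothing to the count. A completed suicide is a death and does count.

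**Size: inputs.**
- n = 15 (Study Summary). More than 3 means at least 4, and 4/15 = 26.7%.
- 2/1000 = 0.20%, from 1.5.1: "Seizures from any kind of rTMS treatment are rare and occur at a rate of about 2/1000". The unit is not stated; I take it as per subject. Read as per session over 15 sessions it would be 1 − 0.998^15 = 3.0% per subject, close to the third figure below.
- 3/209 = 1.44%. Section 3.2 gives 209 subjects tested and three seizures; 1.5.1 gives three in more than 200.
- 3/111 = 2.70%. This is inferred. Section 3.2 gives 111 subjects with psychotropic medication and says: "Of the subjects who were still taking psychotropic medications that could lower seizure thresholds, 3 suffered a seizure". It does not state the ratio, and those taking threshold-lowering drugs may be only some of the 111. Section 4 excludes "Current use of any medications with proconvulsive action" and any increased seizure risk, so 3/111 is probably high for this trial and serves as an upper figure.
- 5%, 10% and 20% are assumptions, to show what happens if the true risk is much higher.

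**Formula.** With independent subjects at equal risk p, all 15 treated and every seizure counted, X is binomial(15, p):

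P(X ≥ r) = Σ from k = r to 15 of C(15, k) p^k (1 − p)^(15 − k).

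Example, p = 3/209 and r = 2: (1 − p)^15 = 0.8050 and 15p(1 − p)^14 = 0.1759, so P(X ≥ 2) = 1 − 0.8050 − 0.1759 = 0.0191.

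| p | At least 1 | At least 2 | At least 4 (stop in 8.4) |
|---|---|---|---|
| 2/1000 | 3.0% | 0.04% | 2 × 10⁻⁸ |
| 3/209 | 19.5% | 1.9% | 0.005% |
| 3/111 (inferred) | 33.7% | 6.1% | 0.06% |
| 5% (assumed) | 53.7% | 17.1% | 0.5% |
| 10% (assumed) | 79.4% | 45.1% | 5.6% |
| 20% (assumed) | 96.5% | 83.3% | 35.2% |

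The first column is the chance that the counting question arises at all. The last is the chance that seizures alone would trigger the stop once they count. Suicide attempts and other serious events would add to it, but the documents give no rate for them.

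**Exposure under a pause at the second seizure.** If subjects are treated one at a time (assumption), the mean number treated is Σ from t = 0 to 14 of P(Bin(t, p) < 2) = 14.998, 14.914 and 14.717 at the first three risks, against 15.000, 15.000 and 14.999 with a stop at the fourth. At these risks a pause saves almost no exposure; its use is as a signal. Two of 15 is 13.3%, with an exact (Clopper–Pearson) 95% interval of 1.7% to 40.5%. The lower limit lies above 0.20% and 1.44% but below 2.70%.

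**The case against.** The strongest reply is that counting these events hardly changes the rule. At the documented or inferred risks the four-subject stop would still almost never be reached, and any lower trigger is a separate design choice. This stands, and it is why the point is minor.

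Seriousness also needs only one positive judgement, from the investigator or the sponsor, in a single-center study run by a sponsor-investigator. Inconsistent counting is therefore a thin worry, and a particular seizure or attempt may well be judged serious. This too stands: the text leaves counting open and does not forbid it. A reader might infer that these events never count; the documents do not support that.

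A reader might also infer that section 4 endorses outpatient care after an attempt. The sentence offering the primary psychiatrist or admission covers both elevated suicide risk and an attempt, and the psychiatrist option may be meant for the former. The suicide part is therefore only possible.

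Finally, other safeguards exist: a physician at each session (1.5.1, 5.4.2), C-SSRS twice a week (3.1), withdrawal (section 4), IRB reporting (8.3.1), expedited FDA reporting of unanticipated device effects (8.3.2), which a cluster of seizures might trigger, and regular review of the number and type of device events (8.5). It would be wrong to infer that study-level oversight is absent. But these act on one subject, require a report, or set no number. The site safety plan could hold a trigger, but it is not in the protocol text: 8.5 points to section 9, which covers data handling, and 10.1 points to section 4, which contains no such plan.

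**Conclusion.** The gap in the text is real and its severity is minor. The one numeric study-level rule can miss the harm that 1.5.1 ranks first and, possibly, suicide attempts that 3.2 also names. Closing it barely changes behaviour at seizure risks of 2/1000 to 3/111 (chance of a stop at most 0.06%). It matters only if the true risk is much higher: 5.6% at an assumed 10%, 35% at an assumed 20%.

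A reader might go on to infer that the threshold of more than 3 subjects is wrong, or that a two-subject pause is required. Neither follows. The threshold is explicit and usable, the documents set no standard that it fails, and the pause is an option for the sponsor.

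The figures rest on per-subject risks, independence between subjects, 15 treated subjects, and 3/111 as an inferred upper figure. The textual conclusion rests on none of these, only on 8.1 being the definition that 8.4 uses.

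**What to change.** Add one sentence to 8.4: *Any seizure, and any suicide attempt after the first rTMS session, counts toward this rule whether or not it meets a criterion in 8.1.* The timing matches section 4, which withdraws a subject for an attempt after receiving rTMS. The stop at more than 3 subjects stays.

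As an option, the sponsor may add a pause in enrolment and in starting new subjects, for review by the sponsor-investigator and the IRB, at a lower count such as a second subject with a seizure. At an assumed 10% risk it would act with probability 45%, against 5.6% for the four-subject stop.

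The first change costs protocol wording only. The option adds a chance of an unneeded pause of 0.04% at 2/1000, 1.9% at 3/209 and 6.1% at 3/111. If the site safety plan already sets such a trigger, citing it in 8.4 is enough.
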